## 1 BACKGROUND AND RATIONALE

### 1.1 Medical Background and Short Rationale for the Clinical Study

Botulinum toxin (BoNT) is a potent neurotoxic protein produced by the Gram-positive anaerobic bacterium, *Clostridium botulinum*. The molecule is produced naturally by these bacteria together with a series of accessory proteins, forming what is termed the “toxin complex”. The neurotoxin is the cause of the severe and potentially fatal disease of botulism. In addition, the protein is used in very small quantities as a treatment modality for aesthetic and medical indications, many of which are characterized by increased muscle activity. Botulinum toxins occur in seven known serotypes (A-G) that are produced by different strains of *Clostridium botulinum*. Clinically important biologic activity is limited primarily to the A and B serotypes, of which the type A serotype (BoNT-A) is used widely throughout the world for the treatment of a range of clinical conditions. BoNT-A blocks the release of acetylcholine into the neuromuscular junction (synapse) cleft, thereby prohibiting the activation of acetylcholine receptors. Paresis by chemical denervation thus occurs in the target muscle, leading to inhibition of muscular contraction.

In the early 1990s, patients treated with BoNT-A for blepharospasm were observed to lose their frown lines, and since publishing these observations, the use of BoNT-A in the aesthetic setting has accelerated. Injectable BoNT-A products have been investigated for multiple aesthetic indications in attempts to reverse the appearance of aging, especially in the facial region. In the treatment of facial lines, the effect of BoNT-A injections usually persists for approximately 4-6 months. Facial muscle activity and severity of the facial wrinkles then returns to baseline. Full functionality of facial muscles is usually restored by approximately 6 months post-treatment.

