#### **7.2.2.2 Reporting Procedures**

##### **7.2.2.2.1 Procedures for Reporting Adverse Events**

The collection of AEs is from the time that a subject signs the ICF to their final visit.

At each post-enrollment visit, the Investigator (or sub-Investigator) will question the subject about AEs using an open non-persuasive question to elicit reporting of AEs, for example “Have you noticed any change in your health since the last visit?” Directed questioning and examination will then be performed as appropriate.

Any AE occurring during the AE reporting period, whether it is related to the study product or not, will be recorded immediately in the source document, and described on the AE form of the eCRF along with the date of onset, severity, relationship to the study product, and outcome, without omitting any requested and known information. Additional information will be requested under certain circumstances.

Adverse Events (AEs) assessed as related to the treatment or study procedure will be monitored until they have resolved or reached a stable condition. Other AEs will be monitored until the last visit if they have not resolved or reached a stable condition.

The Investigator will obtain and maintain in the subject’s files all pertinent medical records, information and medical judgment from colleagues who assisted in the treatment and follow-up of the subject. If necessary, the Investigator will contact the subject’s personal physician or hospital staff to obtain further details.

For SAEs (see Section [7.2.2.2.2](#)) and pregnancies (see Section [7.2.2.2.3](#)), the Sponsor is to be informed immediately by e-mail. The event must be reported by e-mail to the Safety Mailbox within 24 hours of receipt of the information (contact details in Section [7.2.2.2.2](#)).

Effective

Version: 1.0

 GALDERMA	Title 43USD1805 Clinical Study Protocol Dysport New Dilution GL	Doc id [REDACTED]
--	---	----------------------

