### 9.1.3.1 *Safety Analysis*

AEs will be summarized descriptively by treatment group, SOC and PT using number and percentage of subjects with at least one event and number of events. The results will be further broken down by other factors such as severity, causality, seriousness, and whether the event led to discontinuation. Duration and time to onset of related AEs will also be presented by treatment group, SOC and PT.

The numbers and percentages of subjects with abnormalities in physical examination will also be summarized. The results of the urine pregnancy tests will be listed.

All AEs will be monitored by the Sponsor to determine if they meet the criteria of remote spread of effect of the toxin or hypersensitivity. A list of preferred terms for these types of events will be provided in the SAP, and will be further analyzed to determine if there is a plausible possibility that they represent distant spread of toxin or hypersensitivity. In order to perform the analysis, variables including alternative etiology (medical history, concomitant medication, or diagnosis which could account for the symptoms), location of Dysport administration, and temporal relationship to Dysport administration will be considered by the Sponsor.

 Title **43USD1805 Clinical Study Protocol Dysport New Dilution GL** Doc id XXXXXXXXXX

Effective date: 2019-01-24 15:42

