2.5.2 Adverse Events

A summary of all AEs (number and percentage of subjects with at least one event and number of events) by treatment group will be provided, which will include:

- Subjects with at least one AE (in total as well as serious AEs).
- Subjects with at least one treatment-related AE (in total as well as serious AEs).
- Subjects with at least one mild, moderate or severe treatment-related AE (in total as well as serious AEs).
- Subjects with at least one unrelated AE (in total as well as serious AEs).
- Subjects with at least one mild, moderate or severe unrelated AE (in total as well as serious AEs).
- Subjects with at least one AE that led to discontinuation (in total as well as serious AEs).
- Number of subjects who did not have an AE.

All other adverse event tables will also be summarized by treatment. Treatment-related AEs, as well as AEs unrelated to study treatment will be summarized by System Organ Class (SOC), PT and maximum intensity.

In addition, for treatment-related AEs, the number of days to onset and the duration of event will be summarized by SOC and PT.

- Time to onset of an AE will be derived as the start date minus the date of the most recent treatment. If the start date is missing, it will be assumed that the AE started on the day of the most recent treatment. If the start month is available but not the day, it will be assumed that the AE started on the first day of the month.
- Duration of an AE will be derived as the stop date minus the start date + 1. If the start date is missing, it will be assumed that the AE started on the day of most recent treatment. If the start month is available but not the day, it will be assumed that the AE started on the first day of the month. If the stop month is available but not the day, it will be assumed that the AE stopped on the last day of the month. Completely missing stop dates will not be imputed and therefore no duration will be calculated in these cases.

AEs that led to discontinuation from the study will also be summarized.

Serious AEs and treatment-related AEs with late onset (i.e. AEs with onset > 21 days after treatment) will be listed.

For subject counts, a subject will only be counted once per SOC and once per PT in cases where multiple events are reported for a subject within SOC or PT. For event counts, subjects with multiple events in a category will be counted for each event.

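### The AE duration summary in SAP 2.5.2 covers only related events with a stop date, so it understates duration whenever longer-running events are unresolved

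*SAP*

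**What the plan says.** SAP 1.6 lists duration among the AE endpoints. Protocol 9.1.3.1 plans its presentation: "Duration and time to onset of related AEs will also be presented by treatment group, SOC and PT". SAP 2.5.2 carries this out: "for treatment-related AEs, the number of days to onset and the duration of event will be summarized by SOC and PT".

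The formula in SAP 2.5.2 is "Duration of an AE will be derived as the stop date minus the start date + 1". The same section has four rules for incomplete dates. A missing start date becomes the day of the most recent treatment. A start date with only the month known becomes the first of that month. A stop date with only the month known becomes the last day of that month. For a stop date that is wholly absent, "Completely missing stop dates will not be imputed and therefore no duration will be calculated in these cases".

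Protocol 7.2.2.2.1 sets the follow-up. AEs "assessed as related to the treatment or study procedure will be monitored until they have resolved or reached a stable condition". For the rest, "Other AEs will be monitored until the last visit if they have not resolved or reached a stable condition". The same section requires the outcome of each AE to be recorded on the AE form.

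The visible text of SAP 2.5.2 plans no censoring of open events and no count of ongoing events beside the duration summary. It also makes no distinction between an event that is ongoing and one that resolved on an unknown date.

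**The concern.** Whether an event is left out depends on the quantity being measured: the longer a related AE lasts, the more likely it is to have no stop date when data collection ends. A table built only from events with a stop date describes duration among events that ended. It does not describe duration among events that occurred. If a PT has several short events and one that stabilised without resolving, its row shows the short ones alone. The persistent event is probably the one a reader of that row most wants to know about, and the plan's text gives the row no label or count to signal that it is missing.

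The plan treats comparable quantities differently elsewhere. Protocol 9.1.3 and SAP 2.1.2 use Kaplan-Meier estimates for duration of effect and time to onset of response, while open AEs are simply dropped.

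**Working it through.** **1. Which related events lack a stop date.** The last visit does not by itself cause it, because Protocol 7.2.2.2.1 ends follow-up at the last visit only for unrelated AEs, and those are not in the duration summary. Four kinds of related AE remain:

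- stable but not resolved;
- still open at database lock;
- lost to follow-up before resolution;
- resolved, with the stop date unknown.

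The first three are unresolved, and their omission is linked to length. The fourth is ordinary missing data. This reads a stop date as the date the event ended; neither document defines it further.

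**2. Direction.** Let f be the share of related events that are unresolved, m the mean of the resolved events, and U the days already elapsed for the unresolved ones (a lower bound on their true duration). Then

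mean of all events = (1 − f)·m + f·U, so shortfall of the reported mean = f·(U − m).

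This is positive whenever U exceeds m, and zero when f = 0.

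**3. Size, by illustration.** The plan has no figure to reproduce: no AE durations, AE counts or unresolved share are given. Assume that resolved durations are lognormal with median 7 days and sigma 1, rounded up to whole days, so that m is about 12 and the median 7 to 8. Take U from 30 to 168 days; the upper value is Month 6, which SAP 2.1.4 equates with Week 24 (24 × 7 = 168).

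| f | Mean shortfall, U = 30 | Mean shortfall, U = 168 | Median, all events |
|---|---|---|---|
| 0% | 0 | 0 | 7–8 |
| 2% | 0.02 × 18 = 0.4 | 0.02 × 156 = 3.1 | 8 |
| 5% | 0.05 × 18 = 0.9 | 0.05 × 156 = 7.8 | 8 |
| 10% | 0.10 × 18 = 1.8 | 0.10 × 156 = 15.6 | 9 |
| 20% | 0.20 × 18 = 3.6 | 0.20 × 156 = 31.2 | 10 |

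The medians come from simulation. A Kaplan-Meier median with ongoing events censored gives the same 8, 8, 9 and 10 days.

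**4. A worst-case version.** Assume exponential durations with median 30 days, so the mean is 30/ln 2 = 43.3, and let the unresolved fraction q be exactly the longest events. The cut is c = 43.3·ln(1/q), and the retained mean is 43.3 − c·q/(1 − q).

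- q = 10%: c = 99.7, mean 32.2 (26% low), median 25.9.
- q = 20%: c = 69.7, mean 25.9 (40% low), median 22.1.

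**5. Rules that push the other way.** The missing-start, partial-start and partial-stop rules generally lengthen duration or leave it unchanged. Assume that a partial stop date adds 15 days on average. At f = 5% and U = 30, the shortfall of 0.9 days would be cancelled if 0.9/15 = 6% of events had partial stop dates. At f = 5% and U = 168 it would take 7.8/15 = 52%. These rules act on other events and do not restore the omitted ones.

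**The case against.** The best reply is that the affected set may be small or empty. Related AEs are followed beyond the last visit, Protocol 1.4 describes most AEs in the development programme as transient, and Protocol 1.1 says full facial muscle function is usually restored by about 6 months. This stands. It limits how often the problem arises but does not remove it, because a stable, unresolved state is an accepted end of follow-up.

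A reader might take the statement in Protocol 1.1 that the effect on facial lines "usually persists for approximately 4-6 months" as evidence that AEs last as long. The documents do not support that: the sentence concerns efficacy.

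It can also be said that the omission is detectable. SAP 2.1.2 gives the number of subjects with quantitative summaries, all CRF data are listed, and table formats sit in a companion document that is not available here, so an ongoing column may exist. This stands in part. A subject count lower than the incidence count would show that something is absent, but not whether the event was ongoing or merely undated. With several events per subject it need not match the number of events omitted.

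Finally, the sizes above rest on assumed distributions, and medians move little when few events are unresolved. Both points are right.

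**Conclusion.** The rule in SAP 2.5.2 limits the duration summary to related events with a stop date. It will understate duration whenever longer-running related events are unresolved, and it does nothing if all related events resolve with a recorded date. Its size cannot be derived from the documents. In the milder illustration the mean falls short by 0.4 to 31 days and the median by 0 to about 3. In the worst case the mean is 26% to 40% low and the median falls from 30 days to 25.9 or 22.1.

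Two stronger conclusions are tempting and unsupported. One is that AE duration in this trial is understated: that requires unresolved related events, which the documents do not show, and the other date rules pull the opposite way, so the net direction is not fixed. The other is that the arms are affected unequally: this is plausible, since placebo events cannot persist through toxin action, but nothing in the documents measures it.

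The safety analysis is descriptive, and incidence, intensity, causality, seriousness and the listings keep these events. This is a minor reporting improvement.

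**What to change.** Amend SAP 2.5.2 as follows.

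- Use the recorded AE outcome to classify each related event without a stop date as ongoing or as resolved on an unknown date. Do not treat every missing stop date as ongoing, which would misclassify resolved events and could bias duration upward.
- Label the existing summary as covering resolved events with a recorded stop date.
- Beside it, by treatment group, SOC and PT, show the number of related events ongoing, with their minimum duration (last contact minus start + 1), and the number resolved with an unknown stop date.
- Optionally, add a Kaplan-Meier median with ongoing events censored at last contact. Apply it to all rows by a pre-specified rule, so that the estimator does not depend on which rows have open events, and show it as not estimable where the median is not reached. It addresses the median only; the counts and minimum durations reveal what the mean and maximum leave out.

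The cost is an amended paragraph, one or two extra columns and a derived censoring date. Reported durations may become somewhat longer, and Kaplan-Meier medians will often be uninformative in sparse PT rows.

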2.5.3 Adverse Events of Special Interest

Adverse events of special interest (AESIs) for abobotulinumtoxinA are TEAEs that suggest a possible remote spread of effect of the toxin or events suggestive of hypersensitivity like reactions. TEAEs due to possible remote spread of the effects of abobotulinumtoxinA will be identified using the list of MedDRA PTs compatible with the mechanism of action of abobotulinumtoxinA and based on the recommendations from the Committee for Medicinal Products for Human Use (CHMP) and the Food and Drug Administration (FDA). TEAEs potentially representing hypersensitivity reactions will be identified using the Standardised MedDRA Query (SMQ) (narrow search query) for hypersensitivity reactions. A list of MedDRA preferred terms, used to identify any potential AESI, is provided in Section 5.

All TEAEs identified using the search strategy described above will be medically evaluated during the study, before the database lock and unblinding (if applicable), by the sponsor to identify events which could possibly represent 'remote spread of effect of toxin', or which are suggestive of 'hypersensitivity reactions' due to study treatment administration. Cases will be excluded if they are confounded by presence of alternative clinical etiologies (medical history, concomitant medication or diagnosis which could account for the symptoms); if they are considered to be local effects instead of distant spread as judged by the site of injection; the time period between the last study treatment administration and event onset is not in accordance with the expected mechanism of action; or due to insufficient information/evidence to make an assessment. In order to perform the analysis, variables including alternative etiology (medical history, concomitant medication, or diagnosis which could account for the symptoms), location of Dysport administration, and temporal relationship to Dysport administration will be considered.

In the TFLs, only the final list of AESIs confirmed by the sponsor as "a possible remote spread event" or "hypersensitivity reactions" will be taken into account.

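### SAP 2.5.3 applies exclusion grounds suited to toxin spread to hypersensitivity candidates as well, so read literally a local or immediate allergic reaction could drop out of the confirmed count

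*SAP*

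**What the plan says.** SAP 2.5.3 names two AESI types and finds candidates for each by a separate search. Remote-spread candidates come from a list of preferred terms chosen to fit how the toxin acts. For the other type, "TEAEs potentially representing hypersensitivity reactions will be identified using the Standardised MedDRA Query (SMQ) (narrow search query) for hypersensitivity reactions".

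The two streams then merge: "All TEAEs identified using the search strategy described above will be medically evaluated during the study". The sponsor does this before database lock and unblinding. One list of exclusion grounds follows, and it does not separate the two types:

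1. Alternative cause: "Cases will be excluded if they are confounded by presence of alternative clinical etiologies".
2. Local effect: "if they are considered to be local effects instead of distant spread as judged by the site of injection".
3. Timing: "the time period between the last study treatment administration and event onset is not in accordance with the expected mechanism of action".
4. Lack of evidence: "or due to insufficient information/evidence to make an assessment".

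For the outputs, "only the final list of AESIs confirmed by the sponsor" counts. The SAP states no criteria specific to hypersensitivity.

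**The concern.** Location and timing bear differently on the two AESI types. For toxin spread, an effect at the injection site is evidence against remote spread, so a local-effect exclusion makes sense. For hypersensitivity, location does not separate allergic from non-allergic events, because an allergic reaction can be local. Likewise, an onset too early for the toxin to have acted argues against spread but does not argue against allergy.

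The exclusion sentence is mandatory and its subject is simply cases, directly after a sentence covering both types. A medical reviewer who follows it as written could remove a genuine allergic reaction because it was at the injection site, or because it came on too soon for toxin action. Hypersensitivity is one of only two AESI types in the plan, and the AESI outputs carry confirmed cases only, so they would not show that a flagged case had been set aside or why.

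**Working it through.** The documents state no figure on this point and no arithmetic applies. The check sets the passages side by side.

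**Can a local or immediate reaction enter the review?** Yes, if its term is in the search. SAP 1.6 counts an event as treatment-emergent from the time of dosing onward, so a reaction minutes after injection qualifies. Protocol 6.1.7.5 keeps subjects at the center for 30 minutes after treatment, so such reactions can be observed. Protocol 1.4 names injection site reactions among the most frequently reported related events, so local events are to be expected, although the documents do not say how many are allergic.

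**Which grounds fit which AESI type?**

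- Ground 1 (alternative cause) is generic and suits both.
- Ground 2 (local effect) is framed as a contrast with distant spread. It suits spread candidates only.
- Ground 3 (timing) names neither a mechanism nor a time window. The only other use of mechanism of action in SAP 2.5.3 is for abobotulinumtoxinA, in defining the remote-spread term list. The only onset range the documents give for spread symptoms is hours to weeks after injection (Protocol 7.2.2.1.1). If that is the yardstick, a reaction within the 30-minute observation period falls outside it. This ground is probably spread-specific, but that is an inference.
- Ground 4 (lack of evidence) is generic and suits both.

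So of four grounds, one is plainly written for spread, one probably is, and two are general.

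**Does the protocol resolve it?** Protocol 9.1.3.1 also describes one sponsor review for both types. It asks whether spread or hypersensitivity is plausible, and has the sponsor consider alternative cause, location of administration and temporal relationship. It has no rule that a local effect must be excluded. The SAP keeps that list of considerations and adds the mandatory exclusions. Under SAP 2.1 the SAP prevails over the protocol's statistical sections where they differ.

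**What happens to an excluded event?** It leaves the AESI outputs. It stays in the tables of SAP 2.5.2, which summarize related and unrelated events by treatment, system organ class, preferred term and maximum intensity, with days to onset and duration for related events. It also stays in the subject listings under SAP 2.1.2. The SAP describes no output that shows which events the AESI search flagged, which were excluded, or on what ground.

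**The case against.** The strongest reply is that a sensible medical reviewer would not apply the rule this way. The contrast with distant spread only makes sense for a spread candidate, so ground 2 may limit itself. The sentence before the list gives the review a separate aim of identifying likely hypersensitivity reactions, and this is a medical evaluation, not an algorithm. For ground 3, a reviewer could as well ask whether the timing fits an allergic mechanism, since no mechanism is named.

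Much of this stands. A reader might infer that local and immediate allergic reactions will certainly be removed. The documents do not support that: they leave it to the reviewer's reading, and only a literal reading removes them. A reader might also infer that the whole list was written for toxin spread, but two of the four grounds are general. What remains is that a charitable reading is needed to get the right result, and a pre-specified rule should not depend on that.

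A second reply is that nothing is lost. Excluded events remain in the general tables and listings, the review is done before unblinding, and the safety analysis is descriptive with no planned inference. This also stands, and it limits the consequence. It does not remove it: someone wanting the flagged cases would have to rebuild them from preferred terms, and the reasons for exclusion would still be missing.

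**Conclusion.** The point holds in a limited form. The exclusion list in SAP 2.5.3 is undifferentiated, its local-effect ground does not fit hypersensitivity, and its timing ground probably does not either. On a literal reading a local or immediate allergic reaction could be left out of the confirmed hypersensitivity AESIs without any planned AESI output showing it. The consequence is a possible under-count in a descriptive safety subset. It is not a lost event, and it is not a biased test. Because the review precedes unblinding, there is no particular reason to expect exclusions to be made differently by arm on knowledge of treatment.

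No number can be put on it. A reader might try to size the problem from the frequency the protocol gives for eyelid edema, which occurs near the treated area. The documents do not support that. Protocol 1.4 lists it among ocular events and nowhere calls it hypersensitivity, the Section 5 terms are not in the available text, and the sample size is redacted.

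The conclusion on ground 3 rests on taking its mechanism of action to be the toxin's. If the sponsor meant an allergic mechanism for allergic candidates, only ground 2 misfits. This is a cheap improvement to a rule, and the conduct of the trial does not depend on it.

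**What to change.** In SAP 2.5.3:

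- State that the local-effect ground, and the timing ground based on the toxin's mechanism of action, apply to remote-spread candidates only.
- For hypersensitivity candidates, keep the alternative-cause and insufficient-information grounds, and judge temporal relationship against a hypersensitivity reaction instead of toxin action. Limiting exclusion to a documented alternative cause would go too far: it would drop the insufficient-information ground and the temporal relationship that Protocol 9.1.3.1 says will be considered.
- Report search-flagged and confirmed counts side by side by arm for each AESI type, with the reason for each exclusion.

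The cost is one or two SAP sentences and an extra row in the AESI table. No new data are needed and the design does not change. The confirmed hypersensitivity count may rise slightly.
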